### **8.3.2. Vital Signs**

#### **8.3.2.1. Blood Pressure and Pulse Rate**

Supine BP will be measured with the participant's arm supported at the level of the heart, and recorded to the nearest mm Hg after approximately 5 minutes of rest. The same arm (preferably the dominant arm) will be used throughout the study. BP should not be taken from the arm with an intravenous infusion. Participants should be instructed not to speak during measurements.

The same properly sized and calibrated BP cuff will be used to measure BP each time. The use of an automated device for measuring BP and pulse rate is acceptable; however, when done manually, pulse rate will be measured in the brachial/radial artery for at least 30 seconds. When the timing of these measurements coincides with a blood collection, BP and pulse rate should be obtained prior to the nominal time of the blood collection.

Additional collection times, or changes to collection times, of BP and pulse rate will be permitted, as necessary, to ensure appropriate collection of safety data.

Any untoward vital sign findings that are identified during the active collection period and meet the definition of an AE or SAE ([Appendix 3](#)) must be reported according to the processes in [Sections 8.4.1 to 8.4.3](#).

#### **8.3.3. Electrocardiograms**

Standard 12-lead ECGs will be collected at times specified in the [SoA](#) section of this protocol using an ECG system that automatically calculates the HR and measures PR, QT, QTcF, and QRS intervals. All scheduled ECGs should be performed after the participant has rested quietly for at least 5 minutes in a supine position.

To ensure safety of the participants, a qualified individual at the investigator site will make comparisons to baseline measurements. Additional ECG monitoring will occur if a) a postdose QTcF interval is increased by  $\geq 60$  ms from the baseline and is  $>450$  ms; or b) an absolute QT value is  $\geq 500$  ms for any scheduled ECG. If either of these conditions occurs, then 2 additional ECGs will be collected approximately 2 to 4 minutes apart to confirm the original measurement. If the QTcF values from these repeated ECGs remain above the threshold value, then a single ECG must be repeated at least hourly until QTc values from 2 successive ECGs fall below the threshold value that triggered the repeat measurement.

If a) a postdose QTcF interval remains  $\geq 60$  ms from the baseline and is  $> 450$  ms; or b) an absolute QT value is  $\geq 500$  ms for any scheduled ECG for greater than 4 hours (or sooner, at the discretion of the investigator); or c) QTcF value get progressively longer, the participant should undergo continuous ECG monitoring. A cardiologist should be consulted if QTcF values do not return to less than the criteria listed above after 8 hours of monitoring (or sooner, at the discretion of the investigator).

In some cases, it may be appropriate to repeat abnormal ECGs to rule out improper lead placement as contributing to the ECG abnormality. It is important that leads be placed in the same positions each time in order to achieve precise ECG recordings. If a machine-read QTc value is prolonged, as defined above, repeat measurements may not be necessary if a qualified medical provider's interpretation determines that the QTcF values are in the acceptable range.

ECG values of potential clinical concern are listed in [Appendix 8](#).

#### 8.3.4. Clinical Safety Laboratory Assessments

See [Appendix 2](#) for the list of clinical safety laboratory tests to be performed and the SoA for the timing and frequency. All protocolrequired laboratory assessments, as defined in [Appendix 2](#), must be conducted in accordance with the laboratory manual and the SoA. Unscheduled clinical laboratory measurements may be obtained at any time during the study to assess any perceived safety issues.

The investigator must review the laboratory report, document this review, and record any clinically significant changes occurring during the study in the AE section of the CRF. Clinically significant abnormal laboratory test findings are those that are not associated with the underlying disease, unless judged by the investigator to be more severe than expected for the participant's condition.

All laboratory tests with values considered clinically significant and abnormal during participation in the study or within 48 hours after the last dose of study intervention should be repeated until the values return to normal or baseline or are no longer considered clinically significant by the investigator or study medical monitor.

If such values do not return to normal/baseline within a period of time judged reasonable by the investigator, the etiology should be identified and the sponsor notified.

See [Appendix 6](#) for suggested actions and follow-up assessments in the event of potential DILI.

See [Appendix 7](#) for instructions for laboratory testing to monitor kidney function and reporting laboratory test abnormalities.

Participants may undergo random urine drug testing at the discretion of the investigator. Drug testing conducted prior to dosing must be negative for participants to receive study intervention.

#### **8.4. Adverse Events, Serious Adverse Events, and Other Safety Reporting**

The definitions of an AE and an SAE can be found in [Appendix 3](#).

AEs may arise from symptoms or other complaints reported to the investigator by the participant (or, when appropriate, by a caregiver, surrogate, or the participant's legally authorized representative), or they may arise from clinical findings of the investigator or other healthcare providers (clinical signs, test results, etc).

The investigator and any qualified designees are responsible for detecting, documenting, and recording events that meet the definition of an AE or SAE and remain responsible to pursue and obtain adequate information both to determine the outcome and to assess whether the event meets the criteria for classification as an SAE or caused the participant to discontinue the study (see [Section 7.1](#)).

During the active collection period as described in Section 8.4.1, each participant will be questioned about the occurrence of AEs in a nonleading manner.

In addition, the investigator may be requested by Pfizer Safety to obtain specific follow-up information in an expedited fashion.

##### **8.4.1. Time Period and Frequency for Collecting AE and SAE Information**

The time period for actively eliciting and collecting AEs and SAEs ("active collection period") for each participant begins from the time the participant provides informed consent, which is obtained before undergoing any study-related procedure and/or receiving study intervention), through and including a minimum of 28 calendar days, except as indicated below, after the last administration of the study intervention.

Follow-up by the investigator continues throughout the active collection period and until the AE or SAE or its sequelae resolve or stabilize at a level acceptable to the investigator.

When a clinically important AE remains ongoing at the end of the active collection period, follow-up by the investigator continues until the AE or SAE or its sequelae resolve or stabilize at a level acceptable to the investigator and Pfizer concurs with that assessment.

For participants who are screen failures, the active collection period ends when screen failure status is determined.

If the participant withdraws from the study and also withdraws consent for the collection of future information, the active collection period ends when consent is withdrawn.

If a participant permanently discontinues or temporarily discontinues study because of an AE or SAE, the AE or SAE must be recorded on the CRF and the SAE reported using the CT SAE Report Form.

Investigators are not obligated to actively seek information on AEs or SAEs after the participant has concluded study participation. However, if the investigator learns of any SAE,

including a death, at any time after a participant has concluded study participation, and they consider the event to be reasonably related to the study intervention, the investigator must promptly report the SAE to Pfizer using the CT SAE Report Form.

#### **8.4.1.1. Reporting SAEs to Pfizer Safety**

All SAEs occurring in a participant during the active collection period as described in [Section 8.4.1](#) are reported to Pfizer Safety on the CT SAE Report Form immediately upon awareness and under no circumstance should this exceed 24 hours, as indicated in [Appendix 3](#). The investigator will submit any updated SAE data to the sponsor within 24 hours of its being available.

#### **8.4.1.2. Recording Nonserious AEs and SAEs on the CRF**

All nonserious AEs and SAEs occurring in a participant during the active collection period, which begins after obtaining informed consent as described in [Section 8.4.1](#), will be recorded on the AE section of the CRF.

The investigator is to record on the CRF all directly observed and all spontaneously reported AEs and SAEs reported by the participant.

As part of ongoing safety reviews conducted by the sponsor, any nonserious AE that is determined by the sponsor to be serious will be reported by the sponsor as an SAE. To assist in the determination of case seriousness, further information may be requested from the investigator to provide clarity and understanding of the event in the context of the clinical study.

Reporting of AEs and SAEs for participants who fail screening are subject to the CRF requirements as described in [Section 5.4](#).

#### **8.4.2. Method of Detecting AEs and SAEs**

The method of recording, evaluating, and assessing causality of AEs and SAEs and the procedures for completing and transmitting SAE reports are provided in [Appendix 3](#).

Care will be taken not to introduce bias when detecting AEs and/or SAEs. Open-ended and nonleading verbal questioning of the participant is the preferred method to inquire about AE occurrences.

#### **8.4.3. Follow-Up of AEs and SAEs**

After the initial AE or SAE report, the investigator is required to proactively follow each participant at subsequent visits/contacts. For each event, the investigator must pursue and obtain adequate information until resolution, stabilization, the event is otherwise explained, or the participant is lost to follow-up (as defined in [Section 7.3](#)).

In general, follow-up information will include a description of the event in sufficient detail to allow for a complete medical assessment of the case and independent determination of possible causality. Any information relevant to the event, such as concomitant medications

and illnesses, must be provided. In the case of a participant death, a summary of available autopsy findings must be submitted as soon as possible to Pfizer Safety.

Further information on follow-up procedures is provided in [Appendix 3](#).

#### **8.4.4. Regulatory Reporting Requirements for SAEs**

Prompt notification by the investigator to the sponsor of an SAE is essential so that legal obligations and ethical responsibilities toward the safety of participants and the safety of a study intervention under clinical investigation are met.

The sponsor has a legal responsibility to notify both the local regulatory authority and other regulatory agencies about the safety of a study intervention under clinical investigation. The sponsor will comply with country-specific regulatory requirements relating to safety reporting to the regulatory authority, IRBs/Ecs, and investigators.

Investigator safety reports must be prepared for SUSARs according to local regulatory requirements and sponsor policy and forwarded to investigators as necessary.

An investigator who receives SUSARs or other specific safety information (eg, summary or listing of SAEs) from the sponsor will review and then file it along with the SRSD(s) for the study and will notify the IRB/EC, if appropriate according to local requirements.

#### **8.4.5. Environmental Exposure, Exposure During Pregnancy or Breastfeeding, and Occupational Exposure**

Environmental exposure, occurs when a person not enrolled in the study as a participant receives unplanned direct contact with or exposure to the study intervention. Such exposure may or may not lead to the occurrence of an AE or SAE. Persons at risk for environmental exposure include healthcare providers, family members, and others who may be exposed. An environmental exposure may include EDP, EDB, and occupational exposure.

Any such exposures to the study intervention under study are reportable to Pfizer Safety within 24 hours of investigator awareness.

##### **8.4.5.1. Exposure During Pregnancy**

An EDP occurs if:

- A male participant who is receiving or has discontinued study intervention inseminates a female partner.
- A female nonparticipant is found to be pregnant while being exposed or having been exposed to study intervention because of environmental exposure. Below are examples of environmental EDP:
  - A female family member or healthcare provider reports that she is pregnant after having been exposed to the study intervention by ingestion, inhalation, or skin contact.

- A male family member or healthcare provider who has been exposed to the study intervention by ingestion, inhalation, or skin contact then inseminates his female partner prior to or around the time of conception.

The investigator must report EDP to Pfizer Safety within 24 hours of the investigator's awareness, irrespective of whether an SAE has occurred. The initial information submitted should include the anticipated date of delivery (see below for information related to termination of pregnancy).

- If EDP occurs in a participant's partner, the investigator must report this information to Pfizer Safety using the CT SAE Report Form and EDP Supplemental Form regardless of whether an SAE has occurred. Details of the pregnancy will be collected after the start of study intervention and until 28 days after the last dose.
- If EDP occurs in the setting of environmental exposure, the investigator must report information to Pfizer Safety using the CT SAE Report Form and EDP Supplemental Form. Since the exposure information does not pertain to the participant enrolled in the study, the information is not recorded on a CRF; however, a copy of the completed report is maintained in the investigator site file.

Follow-up is conducted to obtain general information on the pregnancy and its outcome for all EDP reports with an unknown outcome. The investigator will follow the pregnancy until completion (or until pregnancy termination) and notify Pfizer Safety of the outcome as a follow-up to the initial report. In the case of a live birth, the structural integrity of the neonate can be assessed at the time of birth. In the event of a termination, the reason(s) for termination should be specified and, if clinically possible, the structural integrity of the terminated fetus should be assessed by gross visual inspection (unless pre-procedure test findings are conclusive for a congenital anomaly and the findings are reported).

Abnormal pregnancy outcomes are considered SAEs. If the outcome of the pregnancy meets the criteria for an SAE (ie, ectopic pregnancy, spontaneous abortion, intrauterine fetal demise, neonatal death, or congenital anomaly in a liveborn baby, a terminated fetus, an intrauterine fetal demise, or a neonatal death), the investigator should follow the procedures for reporting SAEs. Additional information about pregnancy outcomes that are reported to Pfizer Safety as SAEs follows:

- Spontaneous abortion including miscarriage and missed abortion should be reported as an SAE;
- Neonatal deaths that occur within 1 month of birth should be reported, without regard to causality, as SAEs. In addition, infant deaths after 1 month should be reported as SAEs when the investigator assesses the infant death as related or possibly related to exposure to the study intervention.

Additional information regarding the EDP may be requested by the sponsor. Further follow-up of birth outcomes will be handled on a case-by-case basis (eg, follow-up on

preterm infants to identify developmental delays). In the case of paternal exposure, the investigator will provide the participant with the Pregnant Partner Release of Information Form to deliver to his partner. The investigator must document in the source documents that the participant was given the Pregnant Partner Release of Information Form to provide to his partner.

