### 2.3.1. Risk Assessment

Potential Risk of Clinical Significance	Summary of Data/Rationale for Risk	Mitigation Strategy
Study Intervention: PF-07220060		
Potential effects of PF-07220060 on fertility, pregnancy, and lactation.	At this time, it is not known whether PF-07220060 can cause fetal harm when administered to pregnant women. Animal reproductive studies have not been conducted with PF-07220060. It is also not known whether PF-07220060 can affect male or female fertility, or whether PF-07220060 is secreted in human milk. PF-07220060 CCI in rats and dogs on repeat administration and therefore, may potentially impact CCI	Eligibility criteria and the contraceptive lifestyle requirements (duration of caution of contraception CCI days for CCI participants ) for this protocol have been crafted to mitigate these identified potential risks. Participants will be instructed and monitored on the contraceptive requirements implemented to minimize potential risks.
Potential risks associated with PF-07220060 include the following: hematological toxicities (including anemia and neutropenia) and gastrointestinal toxicities (such as nausea, vomiting and diarrhea).	The risks are based on emerging clinical data from the ongoing clinical study C4391001 following continuous administration of PF-07220060 to advanced cancer patients at doses ranging from 100 to 500 mg BID.	The present study will only test single 100 mg oral dose of PF-07220060  AEs and clinical laboratory results will be monitored on an ongoing basis.
Study Procedures		
Exposure to radiation	This study involves using radioactive markers (labels) during oral administration in Cohort 1 and IV infusion in Cohort 2. Radiation may cause side effects including fatigue, hair loss, nausea, vomiting, low blood counts, skin problems and even cancer.	The amount of radiation administered to each participant is very low, CCI nCi, either p.o. or i.v., and below the limit suggested in the FDA Guidance that could be exempted from dosimetry calculations. Based on long-standing experience, the radiation burden will be below 0.1 mSv, ie, ICRP Category I, trivial risk of health damage due to the exposure to ionising radiation.

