Screening will occur within 28 days of the first dose of investigational product. All participants will provide informed consent and undergo screening evaluations to determine their eligibility. Eligible participants will be admitted to the CRU on Day -1. Prior to dosing in both Cohorts, pre-dose urine samples must be collected within 24 hrs prior to dosing and pre-dose fecal samples must be collected within 48 hrs prior to dosing (may be collected at home). The last collected fecal sample will be used as pre-dose sample and all previous pre-dose samples will be destroyed.

Regardless of whether or not the discharge criteria for each cohort have been met, no participant will be confined beyond Day 14 for both Cohorts. The maximum total in-house participation time for each participant in this study is approximately 15 days and 14 nights. Participants will have a follow-up phone call at 28-35 days after the last dose of study intervention.

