## 10.4. Appendix 4: Contraceptive and Barrier Guidance

### 10.4.1. Male Participant Reproductive Inclusion Criteria

Male participants are eligible to participate if they agree to the following requirements during the intervention period and for at least **CC** days after the last dose of study intervention, which corresponds to the time needed to eliminate reproductive safety risk of the study intervention(s) plus an additional 90 days (a spermatogenesis cycle):

- Refrain from donating sperm.

PLUS either:

- Be abstinent from heterosexual or homosexual intercourse as their preferred and usual lifestyle (abstinent on a longterm and persistent basis) and agree to remain abstinent.

OR

- Must agree to use a male condom when engaging in any activity that allows for passage of ejaculate to another person.
- The male participant should be advised of the benefit for a WOCBP partner using a highly effective method of contraception with a failure rate of <1% per year, as described in [Section 10.4.3](#).

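### The 28-day limit on collecting partner-pregnancy details conflicts with the protocol's own male reproductive-risk period of at least 90 days and with its instruction to follow pregnancies to completion

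*Protocol*

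**What the plan says.** **Collection period.** Protocol Section 8.4.5.1, on exposure in a participant's partner, says: "Details of the pregnancy will be collected after the start of study intervention and until 28 days after the last dose". This is the only period with a number of days that the protocol gives for collecting partner-pregnancy details.

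**Same section, other rules.** One way in which exposure during pregnancy (EDP) arises is: "A male participant who is receiving or has discontinued study intervention inseminates a female partner". No end date is attached. On reporting: "The investigator must report EDP to Pfizer Safety within 24 hours of the investigator's awareness, irrespective of whether an SAE has occurred". On follow-up: "The investigator will follow the pregnancy until completion (or until pregnancy termination) and notify Pfizer Safety of the outcome".

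**Risk period.** Section 10.4.1 (Appendix 4) requires male precautions during the intervention period and for a redacted number of days afterwards, "which corresponds to the time needed to eliminate reproductive safety risk of the study intervention(s) plus an additional 90 days (a spermatogenesis cycle". The number is also redacted in Section 2.3.1.

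**Contact.** Section 4.1: "Participants will have a follow-up phone call at 28-35 days after the last dose of study intervention". In both schedules of activities (Section 1.3, Tables 1 and 2) this call, on Day 29-36, is the last scheduled contact and the last scheduled contraception check. Section 5.3.1 has participants told to call at once if pregnancy is known or suspected in a partner, with no end date.

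**Hazard.** Section 2.3.1: "At this time, it is not known whether PF-07220060 can cause fetal harm when administered to pregnant women". It adds that animal reproductive studies have not been done and that effects on male fertility are unknown.

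The SAP gives no rule for pregnancies in its modifications section (2.1) or its safety sections (3.2.3 and 6.2.3).

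**The concern.** The 28-day sentence and the Appendix 4 period both concern paternal exposure after a single dose, yet they differ by at least two months and no reason is given. A site that reads the 28-day sentence literally could close its pregnancy data collection while the participant is still under reproductive precautions.

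With about 12 men dosed, a partner pregnancy would be rare, and each one would be informative because the reproductive hazard is uncharacterised. At stake is the completeness of a small set of safety reports. No endpoint or planned analysis is affected.

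**Working it through.** The plan states no figure to reproduce. The check reads the sentence against its neighbours and then compares the lengths of the periods.

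**Step 1. Two readings of the 28-day sentence**

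| Reading | Consequence | Conflicts with |
|---|---|---|
| It limits which pregnancies are in scope | Pregnancies arising after Day 29 are left out | The undated EDP definition in 8.4.5.1; the period in 10.4.1 |
| It limits how long details are gathered | Collection stops before most pregnancies could reach an outcome | Follow-up to completion or termination in 8.4.5.1 |

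Neither reading agrees with the rest of the protocol.

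**Step 2. Inputs**

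- Dosing is on Day 1 only, in both cohorts, so 28 days after the last dose is Day 29.
- Limit on detail collection: c = 28 days (8.4.5.1).
- Latest follow-up call: c = 35 days after dosing, Day 36 (4.1; Tables 1 and 2).
- Risk period: W = elimination time + 90 days (10.4.1). The total is redacted, so W is at least 90. The values 100 and 120 are assumptions that show the direction of change.

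**Step 3. Share of the risk period after each limit, in days: 1 − c/W**

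| W (days) | After the 28-day limit | After the latest call (35 days) |
|---|---|---|
| 90 (floor) | 90 − 28 = 62 days; 62/90 = 68.9% | 90 − 35 = 55 days; 55/90 = 61.1% |
| 100 | 72 days; 72.0% | 65 days; 65.0% |
| 120 | 92 days; 76.7% | 85 days; 70.8% |

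At the floor, the 28 days cover 28/90 = 31.1% of the period. A larger W makes both shares larger, so 69% and 61% are minimum values.

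**Step 4. What remains in force after the call**

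The participant has completed the study at the last scheduled procedure (4.4). From then on the investigator need not actively seek AEs or SAEs. An SAE that comes to the investigator's notice must be reported if it is considered reasonably related (8.4.1). The duty to report EDP on awareness has no cut-off day (8.4.5.1), and neither does the participant's instruction to call (5.3.1). Reporting therefore stays open but depends on the participant volunteering the information.

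**The case against.** The strongest answer is that the rest of Section 8.4.5.1 already does the work. A conception on, say, Day 50 meets the undated EDP definition. It must be reported within 24 hours of awareness on the safety forms and followed to completion. The same section treats abnormal outcomes as SAEs, allows the sponsor to ask for more information, and provides a release form for the pregnant partner. Section 8.4.1 calls its 28 days of AE collection a minimum. All of this stands: a later pregnancy does not become unreportable.

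Two stronger readings are tempting, and the documents support neither.

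- A reader might infer that most at-risk conceptions escape collection. The 69% is a share of days. Turning it into a share of conceptions needs an even conception rate across the period. The documents give no rate, and abstinence or condom use is required throughout.
- A reader might infer that almost no partner pregnancy would be recorded. That ignores reporting on awareness, and it depends on how soon a pregnancy is recognised, which the documents do not say. If recognition took 14 days (an assumption), a call on Day 29 would reach conceptions up to about Day 15, and one on Day 36 up to about Day 22. The answer moves with the call date as well as with the assumed lag.

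It is also fair to say that the protocol nowhere requires the two periods to be equal, that row order in the risk table does not rank risks, and that the consent pages are not in the copy reviewed, so what participants are told there is unknown. None of this removes the conflict between the 28-day sentence and the follow-up-to-completion text of its own section.

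**Conclusion.** The conflict is real and lies in the protocol's wording. The 28-day sentence agrees neither with the Appendix 4 period nor with the EDP definition and follow-up rule of its own section. At least 69% of the risk period, in days, falls after the stated limit, and at least 55 days fall after the last planned contact.

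These figures rest on two things: a single dosing day, and a 90-day floor inferred from the Appendix 4 formula because the total is redacted. They need no assumption about conception or recognition.

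What lapses is the stated period for collecting details and any active ascertainment, while the duty to report on awareness continues. This is a safety-reporting ambiguity that should be corrected, and it has no bearing on the trial's estimates.

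**What to change.** - Reword the 28-day sentence in Section 8.4.5.1 so that it agrees with Section 10.4.1 and with the section's own definition and follow-up rule. Any partner pregnancy conceived within the Appendix 4 contraception period should be in scope whenever it becomes known, with details collected until the outcome of the pregnancy. Moving the 28-day limit to the end of the contraception period would not be enough: that would still conflict with follow-up to completion and could miss conceptions late in the period that are recognised after it ends.
- State whether active ascertainment continues after the Day 29-36 call or whether later reporting relies on the participant.
- At discharge and at the existing call, remind participants to report any such pregnancy, and check that the consent wording agrees.

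The cost is a short wording change and a later final date for pregnancy reports, in about 12 men. No visit, dose or contraception rule changes.
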